8.5 Analysis Populations

8.5.1 Safety Analysis Population

The safety population will be used for the analysis of safety data in this study. The safety population consists of all subjects who received at least 1 stimulation protocol of trial treatment. Subjects will be included in the treatment group corresponding to the trial treatment they received for the analysis of safety data using the safety population. Subjects who take incorrect trial treatment for the entire treatment period will be included in the treatment group corresponding to the trial treatment received.

At least 1 vital sign measurement obtained after at least 1 stimulation protocol of trial treatment is required for inclusion in the analysis of each specific parameter. To assess change from baseline, a baseline measurement is also required.

8.6 Statistical Methods

Safety and tolerability will be assessed by statistical and clinical review of the following data collected throughout the study: adverse experiences (AEs). Safety will be evaluated with doses combined; selected safety analyses will be performed for doses separately.

The analysis of safety results will follow a tiered approach ([Table 5](#)). The tiers differ with respect to the analyses that will be performed. Safety parameters or adverse experiences of special interest that are identified *a priori* constitute “Tier 1” safety endpoints that will be subject to inferential testing for statistical significance with p-values and 95% confidence intervals provided for between-group comparisons. Other safety parameters will be considered as Tier 2 or Tier 3. Tier 2 parameters will be assessed via point estimates with 95% confidence intervals provided for between-group comparisons.

Membership in Tier 1 requires that at least 4 subjects in any treatment group exhibit the event; all other adverse experiences and predefined limits of change will belong to Tier 2.

Summary statistics for baseline, on-treatment, and change from baseline values will be provided by the treatment group in table format.

See [Table 5](#) for a classification of safety endpoints as Tier 1, or 2 and the corresponding analysis strategy for each endpoint.

Table 5 Analysis Strategy for Safety Parameters

Safety Tier	Safety Endpoint [†]	p-Value [§]	95% CI for Treatment Comparison [§]	Descriptive Statistics
Tier 1	Any AE		X	X
	Any Serious AE		X	X
	Any Drug-Related AE		X	X
	Any Serious and Drug-Related AE		X	X
	Discontinuation due to AE		X	X
	Specific AEs, SOCs, or PDLCs (incidence ≥ 4 subjects in 1 of the treatment groups)		X	X

Tier 2	Specific AEs, SOCs or PDLCs [‡] (incidence <4 subjects in all the treatment groups)			X

² Adverse Event (AE) references refer to both Clinical and Laboratory AEs.
 
³ Includes only those endpoints not pre-specified as Tier 1 or not already pre-specified as Tier-2 endpoint
 
⁴ P-value and CI for safety endpoints based upon Miettinen & Nurminen method
 
Note: SOC=System Organ Class; PDLC=Pre-Defined Limit of Change; X = results will be provided.
				

8.6.1 Summaries of Baseline Characteristics, Demographics, and Other Analyses

8.6.1.1 Demographic and Baseline Characteristics

Demographic variables (e.g., age, gender, race), baseline characteristics, primary and secondary diagnoses, and prior and concomitant therapies will be summarized by treatment either by descriptive statistics or categorical tables.

8.7 Interim Analysis

No interim analyses for efficacy or safety are planned for this study

8.8 Multiplicity

Not planned.

8.9 Sample Size and Power Calculations

Sample size

Sample size: n=60

Power for the primary hypothesis

For a large, standardized effect size (Cohen's $d=0.8$), with a sample size of 52 (26 in each arm) we would have greater than 80% power to detect a significant difference in 9HPT between treatment arms using a two-sample t-test and a two-sided significance level of 0.05. Assuming a common standard deviation of 5.5, this corresponds to a difference of 4.4 units between treatment groups. Allowing for a conservative attrition rate of 15% (our previous trial in SCI with a similar design had 10% attrition⁴⁻⁶), we plan on enrolling 60 participants. Furthermore, as our proposed analysis is a linear mixed-effects model, we anticipate greater efficiency resulting in a slightly higher power. Reimbursement of travel expenses will be used to promote retention.

8.10 Subgroup Analyses

An exploratory sex-stratified analysis will be conducted to assess potential differences in safety and efficacy outcomes between male and female participants. Although the study is not powered to detect sex-specific effects, this analysis aims to provide additional insights into potential sex-related variations in treatment response.

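### Section 8.10 sets out to assess sex differences in treatment response but names only a sex-stratified analysis and no estimate of the difference between the two treatment effects

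*Protocol*

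**What the plan says.** Section 8.10 (Subgroup Analyses) gives the method and the aim together: "An exploratory sex-stratified analysis will be conducted to assess potential differences in safety and efficacy outcomes between male and female participants". It then limits and restates the aim: "Although the study is not powered to detect sex-specific effects, this analysis aims to provide additional insights into potential sex-related variations in treatment response". It says nothing about a model term, a test, a confidence interval or a rule for comparing the sexes.

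No other section supplies the comparison:

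- The efficacy model in the Trial Outline and in Section 8.1 has treatment, time and their interaction as fixed terms, with random intercepts for participant and site. Sex is not in it.
- The sensitivity analysis in Section 8.1 adds a covariate as an independent variable if it is imbalanced at baseline. It names no interaction of that covariate with treatment.
- Section 5.4 stratifies randomization by center only.
- Section 8.8 plans no multiplicity control.

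**The concern.** Whether treatment response varies by sex is a question about the difference between two treatment effects. A stratified analysis estimates each effect separately and leaves the reader to compare them. The usual informal comparison asks which sex reached significance, and that depends heavily on how many men and women were enrolled. A result in the larger group and none in the smaller can arise with identical true effects.

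The power caveat does not settle this. It warns that a real effect within one sex may be missed. It does not supply the quantity that shows how far apart the two effects could be.

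Section 4.1.1 says the pilot should inform the design of pivotal trials, so a clear exploratory statement about sex has some value. A misleading impression of a sex difference would be an avoidable by-product.

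**Working it through.** **Inputs from Section 8.9.** Sample size and power: "with a sample size of 52 (26 in each arm) we would have greater than 80% power". Test and level: "using a two-sample t-test and a two-sided significance level of 0.05". Scale: "Assuming a common standard deviation of 5.5, this corresponds to a difference of 4.4 units between treatment groups". The standardized effect is d = 0.8.

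**Assumptions not in the protocol.** The share of women is 50-75%, balanced across arms and rounded to whole patients. The true effect is the same in both sexes. The calculation uses two-sample t-tests, as Section 8.9 does, so it approximates the planned mixed model.

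**Step 1: reproduce the protocol's figure.** The noncentrality is d x sqrt(n/2) = 0.8 x sqrt(13) = 2.88 on 50 df. Power is 80.7% (82.2% by the normal approximation), which agrees with the stated figure of more than 80%. Also 0.8 x 5.5 = 4.4.

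**Step 2: power within each sex, and the chance that exactly one sex is significant.** Let pF and pM be the noncentral-t powers in women and men. The chance of disagreement is pF(1 - pM) + pM(1 - pF).

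| Women + men per arm | pF, pM at d = 0.8 | Disagree, d = 0.8 | Disagree, d = 0.5 |
|---|---|---|---|
| 13 + 13 | 0.499, 0.499 | 50.0% | 35.6% |
| 17 + 9 | 0.619, 0.358 | 53.4% | 36.3% |
| 18 + 8 | 0.645, 0.320 | 55.2% | 36.7% |
| 20 + 6 | 0.693, 0.241 | 60.0% | 37.8% |

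- Last row at d = 0.8: 0.693 x 0.759 + 0.241 x 0.307 = 0.526 + 0.074 = 0.600. A share of exactly 75% (19.5 + 6.5 per arm) gives 58.7%.
- No effect in either sex: 2 x 0.05 x 0.95 = 9.5%.
- Simulation (40,000 runs) at d = 0.8 gave 50.1%, 53.6% and 55.2% for the first three rows.
- With all 60 patients evaluable, the range is about 49-59% at d = 0.8 and 39-41% at d = 0.5.

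**Step 3: what an estimate of the difference would show.** In SD units, the standard error of the difference between the two effects is sqrt(2/nF + 2/nM), where nF and nM are the numbers per arm. The t quantile on 48 df is 2.011.

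- 13 + 13: sqrt(2/13 + 2/13) = 0.555. Half-width 2.011 x 0.555 = 1.12 SD, or 6.1 units at SD 5.5.
- 20 + 6: sqrt(2/20 + 2/6) = 0.658. Half-width 2.011 x 0.658 = 1.32 SD, or 7.3 units.

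The planned overall effect is 4.4 units, so the interval for the sex difference would extend further on each side than the whole effect the trial is sized to find. For a true sex difference of 0.8 SD, the interaction test has about 29% power at 13 + 13 and 22% at 20 + 6.

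**The case against.** The strongest objection is that this is detail for a separate statistical analysis plan. Section 8.10 gives an aim and a label, and nothing in it rules out an interaction estimate. It also calls the analysis exploratory, says it is not powered and claims only additional insight. That argues against reading non-significance in one sex as absence of effect.

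Much of this stands. A reader might infer that the protocol commits to two separate significance tests and rules out any test of the difference. It does not: Section 8.10 mentions no p-value, level or decision rule within sex, and a descriptive reading is open.

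A reader might also set the 50-60% against the 5% error rate of an interaction test and conclude that the plan carries a 50-60% false-positive rate. That is not supported either. The disagreement rate describes an informal misreading that the protocol does not propose, and it falls with the true effect. The interaction test holds its 5% level but would miss most real differences in a trial of this size.

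The link to the pivotal trials is also indirect, because no section ties later eligibility or stratification to the sex analysis.

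What remains is the mismatch within Section 8.10. The protocol does fix a method here, in a section headed as its statistical analysis plan, and that method does not yield the quantity the aim asks for.

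**Conclusion.** The point holds as a minor one: the stated aim is a between-sex comparison, the stated method is within-sex analysis, and no section names an estimate of the difference.

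The disagreement rates apply only if the within-sex results are read by significance. They rest on 52 evaluable patients, the assumed sex split, a common true effect and the t-test approximation. The 50-60% is one scenario, at the protocol's planning effect. The rates at d = 0.5 and with no effect belong beside it.

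It would be wrong to conclude that adding an interaction lets this trial detect a sex difference. Its benefit is an interval that shows how little can be said. The primary analysis is not affected.

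**What to change.** Reword Section 8.10 along these lines:

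- **Efficacy.** Fit the planned mixed model to all patients with a sex x treatment x time term and its lower-order terms. Report the between-sex difference in the end-of-treatment effect, with its 95% CI, as the exploratory result.
- **Within-sex results.** Show the estimates with CIs as description only, not as evidence for or against a sex difference.
- **Caveat.** State that the interaction also has low power, so an interval that includes zero does not show equal effects.
- **Safety.** Summarise adverse events descriptively by arm and sex.

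The cost is a few sentences and the added model terms. It needs no new data, visits or patients.

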8.11 Compliance (Treatment Adherence)

Summary statistics will be provided on percent compliance by treatment for all subjects included.

8.12 Extent of Exposure

The total number of days each subject received a particular total daily stimulation protocol will be identified and then summarized (as subject counts and percentages)

9.0 LABELING, PACKAGING, STORAGE AND RETURN OF CLINICAL SUPPLIES

No drugs are being tested in this study

10.2 Compliance with Financial Disclosure Requirements

The investigator/subinvestigator(s) agree to provide his/her financial interests to allow for the submission of complete and accurate certification and disclosure statements. The investigator/subinvestigator(s) further agree to provide this information on a Certification/Disclosure Form, commonly known as a financial disclosure form.

10.2.1 Compliance with Ethical Principles and Medical Device Regulation

This study will be conducted in accordance with the ethical principles outlined in the Declaration of Helsinki, as adopted by the 75th World Medical Assembly, Helsinki, Finland, October 2024, and any subsequent revisions.

In addition, the study will comply with all applicable regulatory requirements, including the Regulation (EU) 2017/745 on medical devices, specifically concerning clinical investigations involving medical devices.

The protocol, informed consent forms, and any other relevant study documentation will be reviewed and approved by an independent Ethics Committee prior to initiation. All participants will provide written informed consent before any study-related procedures are performed.

10.3 Compliance with Law, Audit and Debarment

By signing this protocol, the investigator agrees to conduct the trial in an efficient and diligent manner and in conformance with this protocol; generally accepted standards of Good Clinical Practice (e.g., International Conference on Harmonization (ICH) of Technical Requirements for Registration of Pharmaceuticals for Human Use Good Clinical Practice: all applicable federal, state, and local laws, rules and regulations relating to the conduct of the clinical trial.

The Code of Conduct, a collection of goals and considerations that govern the ethical and scientific conduct of clinical investigations, is provided in Section 12.1 Hospital del Mar Neurosciences Code of Conduct for Clinical Trials.

The investigator also agrees to allow monitoring, audits, Ethics Committee review and regulatory authority inspection of trial-related documents and procedures and provide for direct access to all trial-related source data and documents.

The investigator agrees not to seek reimbursement from subjects, their insurance providers or from government programs for procedures included as part of the trial reimbursed to the investigator.

The investigator shall prepare and maintain complete and accurate trial documentation in compliance with Good Clinical Practice standards and applicable federal, state, and local laws, rules, and regulations; and, for each subject participating in the trial, provide all data, and, upon completion or termination of the clinical trial, submit any other reports to the regulatory agencies.

Trial documentation will be promptly and fully disclosed by the investigator upon request and shall be made available at the trial site upon request for inspection, copying, review

and audit at reasonable times from any regulatory authorities. The investigator agrees to promptly take any reasonable steps that are requested because of an audit to cure deficiencies in the trial documentation and worksheets/case report forms.

The investigator must maintain copies of all documentation and records relating to the conduct of the trial in compliance with all applicable legal and regulatory requirements. This documentation includes, but is not limited to, the protocol, worksheets/case report forms, advertising for subject participation, adverse event reports, subject source data, correspondence with regulatory authorities, consent forms, investigator's curricula vitae, monitor visit logs, laboratory reference ranges, laboratory certification or quality control procedures and laboratory director curriculum vitae. By signing this protocol, the investigator agrees that documentation shall be retained until at least 2 years after the last approval of a marketing application in an ICH region or until there are no pending or contemplated marketing applications in an ICH region or until at least 2 years have elapsed since the formal discontinuation of clinical development of the investigational product. Because the clinical development and marketing application process is variable, it is anticipated that the retention period can be up to 15 years or longer after protocol database lock. All trial documents shall be made available if required by relevant regulatory authorities. The investigator must consult with and obtain written approval prior to destroying trial and/or subject files.

ICH Good Clinical Practice guidelines recommend that the investigator inform the subject's primary physician about the subject's participation in the trial if the subject has a primary physician and if the subject agrees to the primary physician being informed.

10.4 Compliance with Trial Registration and Results Posting Requirements

The principal investigator of the trial is solely responsible for determining whether the trial and its results are subject to the requirements for submission to EUDRA (<http://eudragmdp.ema.europa.eu>) or ClinicalTrials.org (<http://www.clinicaltrials.gov>) or other local registries. Hospital del Mar researchers will review this protocol and submit the information necessary to fulfill these requirements. Information posted will allow subjects to identify potentially appropriate trials for their disease conditions and pursue participation by calling a central contact number for further information on appropriate trial locations and trial site contact information.

By signing this protocol, the investigator acknowledges that the statutory obligations under EMA clinical trials directive or other locally mandated registries are that of the investigators and agrees not to submit any information about this trial or its results to those registries.

10.5 Quality Management System

By signing this protocol, the principal investigator agrees to be responsible for implementing and maintaining a quality management system with written development procedures and functional area standard operating procedures (SOPs) to ensure that trials are conducted and data are generated, documented, and reported in compliance with the protocol, accepted standards of Good Clinical Practice, and all applicable federal, state, and local laws, rules and regulations relating to the conduct of the clinical trial.

10.6 Data Management

The investigator or qualified designee is responsible for recording and verifying the accuracy of subject data. By signing this protocol, the investigator acknowledges that his/her electronic signature is the legally binding equivalent of a written signature. By entering his/her electronic signature, the investigator confirms that all recorded data have been verified as accurate. Detailed information regarding Data Management procedures for this protocol will be provided separately.

10.7 Publications

This trial may be intended for publication, even if terminated prematurely. Publication may include any or all the following: posting of a synopsis online, abstract and/or presentation at a scientific conference, or publication of a full manuscript. The principal investigator will work with the authors to submit a manuscript describing trial results within 12 months after the last data become available, which may take up to several months after the last subject visit in some cases such as vaccine trials. Hospital del Mar researchers will post a synopsis of trial results for approved products on EUDRA or Clinicaltrials.gov by 12 months after the last subject's last visit for the primary outcome, 12 months after the decision to discontinue development, or product marketing (dispensed, administered, delivered, or promoted), whichever is later.

These timelines may be extended for products that are not yet marketed, if additional time is needed for analysis, to protect intellectual property, or to comply with confidentiality agreements with other parties. Authors of the primary results manuscript will be provided the complete results from the Clinical Study Report, subject to the confidentiality agreement. When a manuscript is submitted to a biomedical journal, the policy is to also include the protocol and statistical analysis plan to facilitate the peer and editorial review of the manuscript. If the manuscript is subsequently accepted for publication, the researchers will allow the journal, if it so desires, to post on its website the key sections of the protocol that are relevant to evaluating the trial, specifically those sections describing the trial objectives and hypotheses, the subject inclusion and exclusion criteria, the trial design and procedures, the efficacy and safety measures, the statistical analysis plan, and any amendments relating to those sections.

Authorship credit should be based on 1) substantial contributions to conception and design, or acquisition of data, or analysis and interpretation of data; 2) drafting the article or revising it critically for important intellectual content; and 3) final approval of the version to be published. Authors must meet conditions 1, 2 and 3. Significant contributions to trial execution may also be considered to determine authorship if contributions have also been made to all three of the preceding authorship criteria. Although publication planning may begin before conducting the trial, final decisions on authorship and the order of authors' names will be made based on participation and actual contributions to the trial and writing, as discussed above. The first author is responsible for defending the integrity of the data, method(s) of data analysis and the scientific content of the manuscript.

12. APPENDICES

12.1. List of Abbreviations and Definition of Terms

AE	Adverse Experience
ASaT	All Subjects as Treated
βhCG	Beta-Human Chorionic Gonadotropin
BMI	Body Mass Index
BP	Blood Pressure
CI	Confidence Interval
CNS	Central Nervous System
CSR	Clinical Study Report
C-SSRS	Columbia-Suicide Severity Scale
DEGs	Data Entry Guidelines
ALS	Amyotrophic Lateral Sclerosis
ECI	Events of Clinical Interest
eCRF	Electronic Case Report Form
EDC	Electronic Data Capture
FSH	Follicle-stimulating Hormone
TPS	Transcranial Pulse Stimulation
GCP	Good Clinical Practice
HR	Heart Rate

IA	Interim Analysis
IB	Investigator's Brochure
ICF	Informed Consent Form
ICH	International Conference on Harmonization
IEC	Independent Ethics Review Committee
IRB	Institutional Review Board
kg	Kilogram
NCS	Not Clinically Significant
PDLC	Pre-Defined Limit of Change.
PE	Physical Examination

SAC	Scientific Advisory Committee
SAE	Serious Adverse Experience
SAP	Statistical Analysis Plan
SD	Standard Deviation
SES	Standardized Effect Size
SOC	System Organ Class

SOP	Standard Operating Procedure
SAP	Statistical Analysis Plan
ULN	Upper Limit of Normal

12.2. MS Diagnosis Criteria

The diagnosis of MS according to the McDonald criteria requires:

Clinical Presentation	Additional data needed for MS diagnosis
Two or more attacks; objective clinical evidence of two or more lesions	None
Two or more attacks; objective clinical evidence of 1 lesion	Dissemination in space, demonstrated by: 
 • MRI or, • Two or more MRI-detected lesions consistent with MS plus positive CSF or, • Further clinical attack at a different site later
One attack; objective clinical evidence for two or more lesions	Dissemination in time, demonstrated by: 
 • MRI or, • Second clinical attack
One attack; objective clinical evidence of one lesion (monosymptomatic presentation; CIS)	Dissemination in space, demonstrated by: 
 • MRI or, • Two or more MRI-detected lesions consistent with MS plus positive CSF and Dissemination in time, demonstrated by: 
 • MRI or, • Second clinical attack
Insidious neurologic progression suggestive of MS (PPMS)	1-year disease progression (retrospectively or prospectively objectively determined) and two of the following: 
 • Positive brain MRI (nine T2 lesions or four or more T2 lesions with positive VEP) • Positive spinal cord MRI (two focal T2 lesions) • Positive CSF

